### 3. Outcome Measures and Assessments

Outcome measures will be assessed around multiple endpoints. These measures will be: pain, duration of improvement, anticipated observations, and safety. Additional assessments may also be taken but are not considered part of the analysis (i.e. subject post-treatment questionnaire). The specific assessment tools, collection method and time points are listed herein.

#### 3.1.1. Primary Outcome Measure

A decrease in hypertonia as measured by an improvement of 1 point or greater in the Modified Ashworth Scale at Day 7.

Hypertonia will be assessed at each study time period using the Modified Ashworth Scale. Assessment will be conducted by the same Investigator at each time point to reduce inter-assessment variation.

#### 3.1.2. Secondary Outcome Measures

*1.* Improvement in spasticity as measured by the Tardieu Scale: *Subjects will undergo the Tardieu test to assess spasticity (verses stiffness) at each study visit.* 

## CONFIDENTIAL & PROPRIETARY Page 14 of 45

- 2. Improvement in spasm frequency and intensity as measured by the Penn Spasm Score: *Subjects experiencing spasm of the upper extremity will be assessed using the Penn Spasm Frequency Scale at each study visit.*
- 3. Improvement in upper extremity motor recovery as measured by the Fugl-Meyer Scale (post stroke subjects only): Subjects who have spasticity due to stroke will be assessed using the Fugl-Meyer – Motor Recovery after Stroke Scale at each study visit.
- 4. Subject assessed change in Mean Spasticity Numerical Rating Scale (NRS) Score: Subjects will be asked "On a scale of '0 to 10' please indicate the average level of your spasticity over the last 24 hours" with the anchors: 0 = 'no spasticity' and 10 = 'worst possible spasticity'. 'No spasticity' is explained as the time prior to the onset of their spasticity.
- 5. Improvement in pain as assessed by visual analogue scale (VAS): Subjects will be shown a number scale and six facial expressions suggesting various pain intensities. The subject will be asked to choose the face that best describes how they feel. The far left face indicates 'No hurt' and the far right face indicates 'Hurts worst'. The VAS will be conducted at every study visit.

#### **3.1.3.** Ancillary Measures (Potential measures not part of analysis)

Subject Post-Treatment Questionnaire (See Appendix)

#### **3.1.4.** Anticipated Observations (AO) [Data Collection Tool]

During each visit, the area treated will be assessed by the investigator (observation and subject query) for the following anticipated observations (AO's) at the treatment site. These AO's will be collected independent of adverse events and are specific to the treatment site area.

- ecchymosis (bruising)
- edema (swelling)
- erythema (redness or inflammation)
- pain and/or tenderness
- localized dysesthesia (altered sensation)
- thermal injury to the skin, skin lesions, hyper or hypo pigmentation secondary to skin injury
- dimpling of skin

## CONFIDENTIAL & PROPRIETARY Page 15 of 45

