### 1. Introduction

### 1.1.Background

Spasticity, common in neurological disorders, is part of the upper motor neuron syndrome displaying increased tone, clonus, spasms, spastic dystonia and cocontractions. The impact of spasticity on the patient varies from a subtle neurological sign to severe spasticity causing pain and contractures. Upper limb spasticity (ULS) is the rapid contraction or shortening of the muscles in the arm causing abnormal muscle movements in the elbow, wrist and fingers. It has been reported that over 1 million Americans with traumatic injury to the brain or spinal cord, stroke, multiple sclerosis and cerebral palsy experience ULS. Tightly clenched fists, twisted wrist and elbow joints, and fixed arms in flexed positions result in extreme discomfort, pain and spasm. A nonsurgical, minimally invasive, effective approach to pain associated with ULS is desirable.

Myoscience, Inc. (Redwood City, CA) has developed a pain management device – the Cryo-Touch III – for a novel, minimally invasive procedure using focused cold therapy to target sensory nerve tissue and offer long-lasting pain relief through cryoanalgesia. The device operates on the well-established cryobiology principle that localized exposure to controlled, moderately low temperature conditions can alter tissue function. The therapy treats nerves via a probe in the form of an assembly of small diameter needles, creating a highly localized, low temperature treatment zone around the probe. This focused cold therapy creates a conduction block that prevents nerve signaling. Prior studies of the Cryo-Touch, Cryo-Touch II, Cryo-Touch III (a.k.a. PCP 1.0) devices have provided preliminary evidence of effectiveness on motor nerves and have been shown to be safe with no serious device-related adverse events.

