#### 2.6.2. Visit 2/Treatment (Day 0)

#### 2.6.2.1. Pre-Treatment/Evaluation Preparation

No special preparation by the subject is required prior to the treatment. The investigator will reaffirm eligibility criteria and the subject's willingness to continue participation in the trial. Any changes in concomitant medications/concurrent procedures will be recorded. Any adverse events that may have occurred prior to treatment will be documented as a change in medical history.

### **MYOSCIENCE** CONFIDENTIAL & PROPRIETARY Page 11 of 45

The target nerves will be located using adjacent anatomic landmarks. Non-invasive ultrasound imaging of the treatment area may be captured. Nerve stimulation may be used to assess location of nerves via a percutaneous nerve stimulator or a transcutaneous nerve stimulator.

The Cryo-Touch III Device will be used per the Instructions for Use on awake subjects who are prepared with dermal anesthesia only. The skin in the treatment area will be cleansed with alcohol. Local anesthetic will be injected into target sites with the goal of complete cutaneous anesthesia at the target treatment areas prior to the treatment.

The target of treatment are the musculocutaneous nerves (peripheral nerves). The nerves will be treated in a linear fashion to block the nerve at a location deemed appropriate by the investigator (see Figure 3).

Figure 3: Nerve map of intended treatment.

## CONFIDENTIAL & PROPRIETARY Page 12 of 45

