#### 2.6.2.3. Post-Treatment

Upon completion of treatment, the treatment area will be cleansed and the skin will be left undressed. Pressure to the treatment area with gauze for 5-10 minutes may be applied to minimize bleeding. The subject will be instructed in post-treatment care.

The subject will be instructed to report any adverse events or treatment side effects (e.g., excessive redness, swelling, bruising, soreness, altered sensation, etc.) to the investigator between and at follow-up visits. Noninvasive ultrasound may be used to assess the volume and location of the soft tissue treated below the dermis. Photography and/or videography may be obtained.

The subject will be scheduled and instructed regarding their follow-up visits and discharged from the clinic.

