#### 3.2. Adverse Event Reporting

All adverse events, regardless of seriousness, severity, or relationship to device, will be recorded and evaluated by the Investigator. The evaluation will include a determination of the seriousness and severity of the event, whether the event or the severity of the event was anticipated or unanticipated, and the relationship of the event to the study device.

A serious adverse event (SAE) is defined according to ISO14155:2003 (section 3.19) as any adverse event that:

- Led to a death
- Led to a serious deterioration in the health of the subject that
  - resulted in a life-threatening illness or injury
  - resulted in a permanent impairment of a body structure or a body function
  - required in-patient hospitalization or prolongation of existing hospitalization
  - resulted in medical or surgical intervention to prevent permanent impairment to body structure or a body function
- Led to fetal distress, fetal death or a congenital abnormality or birth defect.

An unanticipated adverse device (UADE) effect is defined in 21 CFR 812.3 as any serious adverse effect on health or safety or any life-threatening problem or death caused by, or associated with, a device, if that effect, problem, or death was not previously identified in nature, severity, or degree of incidence in the investigational plan or application (including a supplementary plan or application), or any other unanticipated serious problem associated with a device that relates to the rights, safety, or welfare of subjects.

Events NOT considered to be serious adverse events are:

1) Hospitalizations for the treatment, which was elective or pre-planned, of a preexisting condition that did not worsen; and,

2) Treatment on an emergency, outpatient basis for an event not fulfilling any of the definitions of "serious" given above and not resulting in hospital admission.

Serious Adverse Events and Unanticipated Adverse Device Effects will be reported by the Investigator to myoscience within 24 hours and to the Institutional

CONFIDENTIAL & PROPRIETARY

Page 16 of 45

Review Board (IRB) within the timeframe required by the IRB, but not more than 7 days following the point at which the site becomes aware of the event.

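### The anticipated-observation checklist asks about altered sensation only at the treatment site, although the stated mechanism is block of a peripheral nerve; a broader item would be nearly free

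*Protocol*

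**What the plan says.** Protocol section 3.1.4 sets up a checklist of seven anticipated observations, to be assessed by inspection and by questioning the subject. Its scope is stated in one sentence: the items are kept apart from adverse events and "are specific to the treatment site area". The only sensory item is "localized dysesthesia (altered sensation"). Appendix B schedules this assessment at Visits 2 to 5, the last being the Day 56 telephone contact. Section 3 names anticipated observations among the study's outcome measures.

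On mechanism, section 1.1 says: "This focused cold therapy creates a conduction block that prevents nerve signaling". Section 2.6.2.1 gives the target: "The target of treatment are the musculocutaneous nerves (peripheral nerves"). It leaves the exact place open: "The nerves will be treated in a linear fashion to block the nerve at a location deemed appropriate by the investigator".

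Two other provisions bear on the same symptom. Section 2.6.2.3 tells subjects to report side effects, and its examples include altered sensation: "e.g., excessive redness, swelling, bruising, soreness, altered sensation, etc.) to the investigator between and at follow-up visits". Section 3.2 says: "All adverse events, regardless of seriousness, severity, or relationship to device, will be recorded and evaluated by the Investigator".

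**The concern.** Bruising, swelling and skin injury occur where the probe goes in, so a checklist confined to the site suits them. Altered sensation is different. If the treatment stops a nerve from conducting, any sensory change can appear in the region that the nerve supplies, which need not be where the probe was placed. The one item that asks about sensation is restricted to the site.

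What is at stake is the safety description of a small study in a population that section 2.1 calls contraindicated under current labeling and section 4.2 calls not previously studied. The same nerve effect would be an AO if felt at the site and, if mentioned at all, an adverse event if felt elsewhere. Section 3.1.4 keeps these two streams apart, so neither tally alone gives the frequency of altered sensation.

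**Working it through.** The plan gives no rate of altered sensation, so there is no figure to reproduce. The check is to list every route by which the symptom could be captured and see what each one reaches.

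| Route | Asks about or tests sensation? | Reaches beyond the site? | Subjects | When |
|---|---|---|---|---|
| AO checklist (3.1.4, Appendix B) | Yes, one item | No | All | Visits 2 to 5 |
| Instruction to report side effects (2.6.2.3) | Named as an example; relies on the subject to speak up | No limit stated | All | Given after treatment |
| Adverse event review (3.1.5, 3.2, Appendix B) | No symptom named | Yes under 3.1.5 and 3.2; unclear under 2.6.3 and 2.6.4 | All | Visits 2 to 5 |
| Fugl-Meyer sensory form (Appendix C) | Yes, light touch and proprioception | Partly | Stroke only | Visits 1 to 4 |
| Post-treatment questionnaire (Appendix D) | No; asks about pain from the treatment | No limit stated | All | Days 7 and 30; not analysed (3.1.3) |

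Four things follow.

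1. **Prompting.** Only the first and fourth routes ask about or test sensation on a schedule. The first stops at the site. The fourth covers stroke subjects only. Its light-touch areas are upper arm, palm, thigh and sole, so the arm is represented by upper arm and palm. Proprioception is tested in the arm at shoulder, elbow, wrist and thumb. Subjects whose spasticity comes from cerebral palsy, multiple sclerosis or brain injury have no scheduled sensory test.

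2. **Adverse event wording.** Sections 3.1.5 and 3.2 set no limit by location. Sections 2.6.3 and 2.6.4, which tell the site what to do at Day 7, Day 30 and Day 56, list anticipated observations, adverse events and serious or unanticipated events, and then tie them to the previously treated site. That qualifier may be meant for the whole list or only for its last entry. On the first reading, the follow-up instruction is narrower than section 3.2.

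3. **Baseline.** Appendix B has no AO assessment at Visit 1 and does not say whether the one at Visit 2 comes before or after treatment, although it does say so for the pain scale. Medical history and a physical examination are scheduled, but no sensory content is named. The conditions enrolled may themselves alter sensation, so a later report may have nothing to be compared with.

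4. **Scale.** The number of subjects with altered sensation away from the site is unknown. The weight of each one is known: with 10 to 20 subjects (section 2.3), one subject missing from the tally changes the proportion by 1/20 = 5 to 1/10 = 10 percentage points.

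**The case against.** The strongest reply is that the split is deliberate. The checklist logs local reactions, and everything else goes to adverse event review, which is scheduled at Visits 2 to 5 and is unrestricted under sections 3.1.5 and 3.2. Subjects are told to report altered sensation, with no limit by place. Numbness in the forearm therefore has somewhere to be recorded, with severity and relationship assessed. This stands, and it rules out some stronger readings.

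A reader might infer that altered sensation is looked for in the wrong place. The documents do not support that: altered sensation at the probe site is a legitimate item, and the fault is that the item is narrow. A reader might also infer that a persisting deficit will go unrecorded, or that the overall rate will be too low. That would require the adverse event route to fail as well, and nothing in the protocol shows that it will.

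It can also be said that the protocol text never describes the skin territory of the nerve, that the nerve map (Figure 3) is not shown, and that the Instructions for Use and case report forms, which may carry further prompts, are not at hand. This is fair. The documents do not support calling a change in one particular region the most predictable effect. The narrower point needs only the stated mechanism, and section 1.1 itself describes the device as aimed at sensory nerve tissue.

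The argument that no outcome depends on the item does not stand, because section 3 counts anticipated observations as an outcome measure.

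**Conclusion.** The point holds in a limited form. The AO checklist does not prompt for altered sensation beyond the treatment site. Capture there depends on general adverse event review and spontaneous report, plus, in stroke subjects only, a sensory form with limited coverage of the arm. The AO tally may therefore understate altered sensation. For the safety data as a whole this is a risk and not a demonstrated loss, and its size cannot be derived from the documents.

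This rests on two assumptions. One is that the treated nerve carries sensory fibres to areas beyond the probe site; this fits the stated mechanism but is not spelled out in the text. The other is that the case report forms carry no prompts beyond those the protocol describes. The mismatch between sections 2.6.3 and 2.6.4 and sections 3.1.5 and 3.2 needs neither assumption. Overall, this is a cheap improvement to safety capture and does not threaten the primary outcome.

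**What to change.** - Reword the sensory item in section 3.1.4 to *altered sensation anywhere in the treated limb*, with a tick for location (treatment site, forearm, hand), and adjust the sentence that confines the checklist to the site.
- Ask the item before treatment, and at each later contact already scheduled, including the telephone contacts. The Day 56 call already includes an AO assessment.
- Reconcile the site-limited adverse event wording in sections 2.6.3 and 2.6.4 with the unrestricted wording in sections 3.1.5 and 3.2.
- State whether a tick away from the treatment site is also recorded as an adverse event. Widening the list otherwise moves such changes into a stream that is kept separate from adverse events.

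The cost is one reworded item, one added tick field, one pre-treatment question and an edit to two sections. No new visit or test is needed. The reported frequency of altered sensation may rise. The location tick lets the site-only count still be reported, and the pre-treatment answer helps to separate new changes from existing ones.

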#### **3.1.5.** Safety Measures [Data Collection]

Adverse events and SAEs/UADEs will be assessed at all visits. Incidence of serious adverse events (SAEs) and unanticipated adverse device effects (UADEs) will be recorded.

#### 3.2. Adverse Event Reporting

All adverse events, regardless of seriousness, severity, or relationship to device, will be recorded and evaluated by the Investigator. The evaluation will include a determination of the seriousness and severity of the event, whether the event or the severity of the event was anticipated or unanticipated, and the relationship of the event to the study device.

A serious adverse event (SAE) is defined according to ISO14155:2003 (section 3.19) as any adverse event that:

- Led to a death
- Led to a serious deterioration in the health of the subject that
  - resulted in a life-threatening illness or injury
  - resulted in a permanent impairment of a body structure or a body function
  - required in-patient hospitalization or prolongation of existing hospitalization
  - resulted in medical or surgical intervention to prevent permanent impairment to body structure or a body function
- Led to fetal distress, fetal death or a congenital abnormality or birth defect.

An unanticipated adverse device (UADE) effect is defined in 21 CFR 812.3 as any serious adverse effect on health or safety or any life-threatening problem or death caused by, or associated with, a device, if that effect, problem, or death was not previously identified in nature, severity, or degree of incidence in the investigational plan or application (including a supplementary plan or application), or any other unanticipated serious problem associated with a device that relates to the rights, safety, or welfare of subjects.

Events NOT considered to be serious adverse events are:

1) Hospitalizations for the treatment, which was elective or pre-planned, of a preexisting condition that did not worsen; and,

2) Treatment on an emergency, outpatient basis for an event not fulfilling any of the definitions of "serious" given above and not resulting in hospital admission.

Serious Adverse Events and Unanticipated Adverse Device Effects will be reported by the Investigator to myoscience within 24 hours and to the Institutional

CONFIDENTIAL & PROPRIETARY

Page 16 of 45

Review Board (IRB) within the timeframe required by the IRB, but not more than 7 days following the point at which the site becomes aware of the event.

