# CONFIDENTIAL & PROPRIETARY

Page 10 of 45

- 4. Allergy or intolerance to local anesthesia.
- 5. Any local skin condition at the treatment site that in the investigator's opinion would adversely affect treatment or outcomes.
- 6. Any chronic medication use (prescription, over-the-counter, etc.) that in the investigator's opinion would affect study participation or subject safety.
- 7. Diagnoses of cryoglobulinemia, paroxysmal cold hemoglobinuria, cold urticaria, Raynaud's Disease, open and/or infected wounds.
- 8. Diagnoses of progressive neurologic diseases such as ALS.
- 9. For any reason, in the opinion of the investigator, the subject may not be a suitable candidate for study participation (i.e., history of noncompliance, drug dependency, any related upper limb injury, etc.).

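### Section 3.2 asks for causality against the device only, so events caused by the anesthetic injection or nerve stimulation cannot be separated from unrelated events

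*Protocol*

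**What the plan says.** Section 3.2 of the protocol opens with a broad capture rule: "All adverse events, regardless of seriousness, severity, or relationship to device, will be recorded and evaluated by the Investigator". It then lists what the investigator determines for each event: seriousness, severity, whether the event was anticipated, and "the relationship of the event to the study device". No other causal question appears in the protocol.

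The device is described in section 1.2 by its parts: control unit, handpiece, single-use cryoprobes and cryogen cartridges.

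The treatment visit contains more than the device. Section 2.6.2.1 says: "Local anesthetic will be injected into target sites with the goal of complete cutaneous anesthesia". That step is planned for every subject. The same section adds an optional step: "Nerve stimulation may be used to assess location of nerves via a percutaneous nerve stimulator or a transcutaneous nerve stimulator". Exclusion 4 in section 2.5 ("Allergy or intolerance to local anesthesia") shows that exposure to the anesthetic was considered when the population was chosen.

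The named safety measures in section 3.1.5 are the incidence of serious adverse events and of unanticipated adverse device effects. Section 3.1.4 collects local reactions at the treatment site as anticipated observations, separately from adverse events and with no causality step.

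**The concern.** A subject receives the anesthetic injection, and sometimes the percutaneous stimulation, only because of the study treatment. If one of these steps alone causes a systemic reaction or a nerve injury, the investigator is asked only whether the device did it. Read against the parts list in section 1.2, a literal answer is no. The same answer would be given for an unrelated illness, so the data would not distinguish the two.

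This matters more than usual because the study has a single group of 10 to 20 subjects, with no control arm to show what the preparation contributes. Section 4.2 says the population has not been studied before. Section 1.1 summarises the safety of earlier studies as an absence of serious device-related events. If this study is summarised in the same terms, harm from the preparation steps would be missing from that summary.

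**Working it through.** The protocol gives no adverse event rate, no related-event rate and no causality scale, so there is no stated figure to reproduce. The check is a comparison of sections, followed by one piece of arithmetic.

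**Sections side by side**

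| Step in the treatment visit | Planned for | Part of the device in section 1.2? | Causality judgment in section 3.2 |
|---|---|---|---|
| Cryoprobe insertion and cooling cycle | every subject | yes | relationship to device |
| Local anesthetic injection (2.6.2.1) | every subject | no | none of its own |
| Percutaneous nerve stimulation (2.6.2.1) | optional; a transcutaneous alternative is named | no | none of its own |

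Probe insertion belongs in the first row, because section 1.2 makes it the start of each cooling cycle. The gap therefore concerns the last two rows only.

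The protocol's own wording is uneven on this point. The exit reminder in section 2.6.4 asks subjects to report later events related to the treatment, whereas section 3.2 has the investigator judge the device.

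**What does and does not change**

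- Count of all adverse events: unchanged, since section 3.2 records every event.
- Incidence of serious adverse events: unchanged, since it does not depend on cause.
- Unanticipated adverse device effects: may be affected, since the definition in section 3.2 requires a link to a device. Such an event would still be reported as a serious adverse event.
- Any tabulation of device-related events: may be affected.

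**Size per subject**

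Inputs: N from 10 to 20 (section 2.3). Assumption: one subject's only related event is caused by the injection or the stimulation and is coded not device-related.

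Shortfall of the device-related proportion against the device- or procedure-related proportion = 1/N.

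- N = 20: 1/20 = 5 percentage points.
- N = 10: 1/10 = 10 percentage points.

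The number of such subjects is not in the documents and may be zero.

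**The case against.** A reader might infer that section 3.2 makes investigators class harm from the injection or stimulation as unrelated, and so removes it from the study's related-event rate. The documents do not support that. Section 3.2 contains no such instruction and no definition of related, and its list of judgments is not stated to be exhaustive. Section 2.6.2.1 presents the anesthesia as preparation for using the device ("The Cryo-Touch III Device will be used per the Instructions for Use on awake subjects who are prepared with dermal anesthesia only"), so an investigator could reasonably call such an event device-associated. The protocol also defines no related-event rate. How events are tabulated is commonly left to an analysis plan, which is not at hand.

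Much of the local harm is captured anyway. Bruising, swelling, tenderness and altered sensation at the treatment site are collected as anticipated observations whichever needle caused them. Serious events go to the sponsor within 24 hours whatever their cause. With at most 20 subjects, reviewing events one by one afterwards looks feasible. Exclusion 4 concerns who may enter and says nothing about attribution.

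These points stand, and they limit the concern. They do not remove it. If one investigator may call an anesthetic reaction device-associated and another may not, the same event can be coded two ways, which is itself a reason for an explicit field. The anticipated observations are a list of site reactions and do not include systemic anesthetic reactions. An analysis plan can choose the tabulation, but it cannot supply a judgment that the form never asked for. A later review would have to reconstruct that judgment from whatever was written down.

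**Conclusion.** The point holds in a narrow form and is minor. Causality is collected against the device alone, while every treatment includes an anesthetic injection and some may include percutaneous stimulation, both outside the device as described. Events caused only by those steps are recorded but cannot be distinguished from unrelated events. A summary of device-related events may then understate the harm of the treatment as delivered, by 5 percentage points per affected subject with 20 subjects and by 10 with 10.

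This rests on two assumptions that the protocol does not settle: that at least one such event occurs, and that the investigator reads the device literally as section 1.2 describes it. It also matters only if results are summarised as device-related events, as section 1.1 does for earlier studies. Counts of all adverse events and of serious adverse events are sound as planned.

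**What to change.** In section 3.2, extend the causality item to read: "the relationship of the event to the study device" *and, separately, to the study procedure (anesthetic injection, nerve stimulation)*. Probe insertion stays with the device, in line with section 1.2. Report device-related events, and device- or procedure-related events, beside all adverse events.

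The cost is one extra field on the adverse event form and one line in section 3.2. The reported related-event rate may be somewhat higher. Clinical management does not change.
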